# **Stopping rules**

The occurrence of an unexpected include implant failure...

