# Sample Size:

Twenty single-piece endosseous implants use for patients with at least two missing teeth in the upper or lower jaw (canine to 1st molars area).

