# **Procedure:**

Twenty single-piece endosseous implants (Dentium Co, Korea) will use to restore missing teeth in the upper or lower jaw (canine to 1st molars area) from both sides. The study will be split-mouth technique, each patient serves as his own control (served into 2 groups), the study side (topical application of melatonin in the implant side), and the control side (no melatonin in the other implant side of the same patients). According to the study reported by **(Cutando et al., 2008)** the estimated dose of melatonin required to enhance osseointegration of dental implant and minimize the marginal bone resorption is 1.2 mg of melatonin powder for each implant. CBCT for all patients before implant placement to determine bone density, dimension, and anatomical landmarks. Prior to surgery, all patients will instruct to use chlorhexidine 0.12% mouthwash as antiseptic. After local anesthesia, a mucoperiosteal flap will reflect. The manufacturer's instructions should be followed for the preparation of the implant osteotomy site. For the study

side, 1.2 mg of melatonin powder will place in the osteotomy site before the insertion of the implant. For the control side, no melatonin powder will be used and implants will be inserted directly in the prepared implant site. After dental implant installation, the gingival former will insert into the body of the fixture, then the Periotest M device will use to measure the primary stability of the DI fixture. After that, the gingival former will be removed and cover screw place and tightened into the fixture. Sutures will place after flap replacement. Patients should be instructed to use antibiotics amoxicillin 500mg and metronidazole 500mg 3 times/day for 5 days after surgical procedure, soft diet and proper oral hygiene measures. Also, CBCT immediately after implant placement to record baseline bone level, CBCT after 6 months follow up to measure marginal bone level around implant comparing with baseline measurement, and measure the secondary stability using periotest M device.

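### Does the unfinished stopping rule, whose one named event is next examined on schedule at six months, call for a change to the plan?

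*Protocol*

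**What the plan says.** The Stopping rules section of the protocol is one fragment: "The occurrence of an unexpected include implant failure", followed by an ellipsis. No noun follows the adjective, and no threshold, action or decision-maker is given. No redaction is marked there, although a word lost when the PDF was read cannot be excluded.

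The schedule comes from the Procedure section:

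- **At surgery, once, study side only:** "1.2 mg of melatonin powder will place in the osteotomy site before the insertion of the implant".
- **Same day, stability:** "then the Periotest M device will use to measure the primary stability of the DI fixture".
- **Same day, closure:** "the gingival former will be removed and cover screw place and tightened into the fixture", after which the flap is sutured.
- **Same day, imaging:** "CBCT immediately after implant placement to record baseline bone level".
- **Next examination named:** "CBCT after 6 months follow up to measure marginal bone level around implant comparing with baseline measurement", with the secondary stability reading in the same sentence. None is named after it.

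The Sample Size section gives the number of implants but not of patients: "Twenty single-piece endosseous implants use for patients with at least two missing teeth in the upper or lower jaw". Table 1, in the Periotest M section, gives bands for stability readings; the highest, +10 to +50, means insufficient osseointegration. The protocol does not connect that table to the stopping rule.

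**The concern.** Two things look wrong. First, the sentence cannot be applied as written. Two readers could act on the same failed implant in opposite ways, one withdrawing the patient and the other ending the trial.

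Second, the rule seems not to fit the schedule. Melatonin is given once, and the next listed look at the implant is also the last. By then there is nothing left to stop in that patient, so only a trial-level reading has any effect, and the section does not state one.

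If the meaning were settled only after a failure, some six-month results might already be known. The number of pairs analysed could then depend on those results, which would raise the false-positive rate and could cost power in a very small trial.

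**Working it through.** The stopping rule contains no figure to reproduce. The check has two parts: the text, and how much the gap could matter.

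**Text**

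1. *What counts as failure.* Undefined. The Periotest bands in Table 1 are an obvious candidate, but they are not linked to the rule.
2. *When failure could be seen.* Stability and imaging are recorded on the day of surgery, so a failure at placement could be seen then. The next listed examination is at six months.
3. *Whether that list is a visit calendar.* It reads as a list of outcome measurements. The implant is covered at surgery and has to be uncovered before the six-month Periotest reading, yet uncovering is not listed. Silence about other contacts therefore does not show that there are none. That failure is first looked for at the last visit is an inference.
4. *Whether stopping is tied to outcomes.* The protocol describes no interim analysis and no stop based on stability or bone-level differences.

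**Size**

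Inputs: 20 implants (Sample Size). Assumed, because the protocol gives no such figures: 10 patients with one pair each, a paired t-test at two-sided 5%, and a failure probability *p* of 1-5% per implant.

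*Chance of any failure*

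| *p* | Independent: 1 − (1 − *p*)^20 | Pair fails together: 1 − (1 − *p*)^10 |
|---|---|---|
| 1% | 18.2% | 9.6% |
| 2% | 33.2% | 18.3% |
| 5% | 64.2% | 40.1% |

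*Precision.* The difference detectable with 80% power, in SDs of the paired differences, and the power at 1.0 SD:

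| Pairs | Detectable difference | Power at 1.0 SD |
|---|---|---|
| 10 | 1.00 SD | 80% |
| 9 (failed pair lost) | 1.07 SD | 75% |
| 4 (trial ends at the fifth patient's six-month visit) | 2.13 SD | 29% |

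The 4-pair row requires that patients already operated on are not followed to six months. The protocol does not say that. Suppose surgery *k* takes place at (*k* − 1) × *E*/9 months, where *E* is the assumed enrolment period.

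- With *E* = 12, the fifth patient's visit falls at 4 × 12/9 + 6 = 11.3 months. Patients with (*k* − 1) × 12/9 ≤ 11.3, that is *k* ≤ 9, have been operated on, so 9 − 1 = 8 pairs remain if enrolment stops and follow-up continues.
- With *E* ≤ 6, all 10 have been operated on before any six-month visit is completed, so 9 pairs remain.

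*False-positive rate.* Suppose a result counts as positive if p < 0.05 either at the *m* pairs complete when the first failure appears or at all 9 non-failing pairs. Simulation under the null (1,000,000 runs) gives:

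| *m* | 2 | 3 | 4 | 5 | 6 | 7 | 8 |
|---|---|---|---|---|---|---|---|
| Rate | 9.6% | 9.3% | 9.0% | 8.5% | 8.0% | 7.5% | 6.7% |

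The chance that the first failing pair comes after *m* complete pairs is *q*(1 − *q*)^*m*, where *q* is the chance that a pair fails. Weighting each excess over 5% by this chance (no excess at *m* = 0, 1 or 9):

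- *p* = 1%, pair fails together (*q* = 0.01): weights 0.0098 to 0.0092, weighted excess 0.23 points, rate 5.2%.
- *p* = 5%, independent (*q* = 1 − 0.95² = 0.0975): weights 0.079 to 0.043, weighted excess about 1.5 points, rate 6.5%.

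So 9% is the rate given a failure at one particular point and an investigator who chooses by p-value. Over the assumed range the average is 5.2-6.5%.

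**The case for a change.** The strongest case for a change is that this is not simply silence. The protocol has a stopping-rules section, and that section is broken. One lost word would not supply the definition, the side, the level and the action. With 20 implants a single failure is plausible, and completing the text would cost only wording. Two short statements would also close the statistical opening: that a stop for failure is decided without reference to the accumulated outcome differences, and that every pair with six-month data is analysed.

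Much of this stands. The sentence is incomplete, no other section completes it, and no examination is named between the day of surgery and six months.

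What does not stand is the step from there to a statistical defect. A trial-level reading is an ordinary one for a section with this heading, so single dosing does not make the rule useless; it only shows again that the level is unstated. The statement about which pairs are analysed defines the analysis set, which commonly sits in a statistical analysis plan, and none is at hand here. Deciding a safety stop without looking at efficacy differences is normal practice, and the protocol says nothing to the contrary. The larger figures, 9.0% and 29% power, each need several assumptions to hold together: the patient count, the test and the timing of the failure. The first also needs a results-driven choice, and the second needs follow-up to be abandoned.

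**Conclusion.** No change to the plan follows. The Stopping rules section is an unfinished fragment, and a failure first found at the six-month examination could affect only the rest of the trial. Earlier unscheduled detection, or detection at placement, is not excluded.

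This is a gap that the investigator would be expected to fill sensibly. What counts as failure, and what follows from it, is clinical content on which this review takes no position. When the sentence is completed, it should be reconciled with the Periotest table and the Procedure schedule.

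A failure is a realistic event: 18-64% if implants fail independently, 10-40% if pairs fail together, at assumed rates of 1-5% per implant and 10 assumed pairs. The statistical consequence is small. It arises only if someone decides by looking at the results, and even then the average false-positive rate is 5.2-6.5%. If follow-up of operated patients continues, 8 or 9 pairs remain in the enrolment patterns considered, not 4. All these sizes rest on a patient count, a test, failure rates and an enrolment pattern that the protocol does not give.

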# **Budget and funding**

This study is self-funded.

### Justification for ethical approval:-

According to the college of the dentistry/university of Baghdad following the Declaration of Helsinki / Tokyo on medical protocol and ethics.

#### Dissemination

Postgraduate Thesis.

